Patients with stable (no relapses for the previous 90 days) relapsing form of MS, being treated with interferon beta1a or 1b, glatiramer acetate, fingolimod, dimethyl fumarate or teriflunomide for at least 6 months, with Expanded Disability Status Scale (EDSS) scores of 4 or less, Modified Fatigue Impact Scale (MFIS) score of 38 or greater, or a Fatigue Severity Scale (FSS) score of 36 or greater, Beck Depression Inventory-II (BDI-II) score of 19 or less, and Epworth Sleep Score (ESS) of 9 or less. Subject will be excluded if he or she has attempted suicide in the past, has current suicidal thinking based on the Columbia Suicide Severity Rating Scale (C-SSr), or is preparing for suicide. History must be negative for difficulty sleeping, sleep apnea, painful nocturnal spasms, nocturnal neuropathic pain, and restless leg syndrome, history of psychosis or neuroleptic use, have no evidence of current hypothyroid state, use of cannabis, opiates, benzodiazepines, or other gaba-ergic medications except baclofen or tizanidine. Subjects cannot have received corticosteroids of any type for 90 days prior to baseline visit. Subjects must not have any of the contraindications for Acthar Gel as listed in the approved label, including sensitivity to proteins of porcine origin. Subject must agree not receive any live or live-attenuated vaccine during the trial. Ninety subjects will be recruited and randomized 1:1 to receive ACTH or placebo in a subject and examining physician-blinded manner. The sample size was calculated by a power analysis for a two-sided test with $\alpha=0.05$ and power = 0.80 and assuming a 20% dropout rate.

Subjects will be randomized in groups of 4, with equal number of placebo and ACTH treated patients in each 4-subject group. In order to reach enrollment target in 12 months, full competitive enrollment will be applied until the enrollment goal is fulfilled.

The study protocol, informed consent forms (ICF), and case report forms (CRF) must be approved by the organization's institutional review board or appropriate ethics committee. Site investigators will obtain written informed consent to participate from eligible patients prior to screening or any study procedures taking place. A copy of the ICF will be given to the patient and the original ICF and the documentation of the consent process will be kept in the patient's record at each site.

Inclusion Criteria

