Candidates must fulfill **all** of the following criteria before being included in the study:

1. Have documented diagnosis of Relapsing MS as defined by McDonald Criteria 2011 Revision for at least 6 months
2. Age range of 18 to 65 years old, inclusive at time of screening
3. Have been treated with interferon beta 1a or 1b, glatiramer acetate, fingolimod, dimethyl fumarate or teriflunomide for at least 6 months, with reported adherence rate of at least 75%, at time of screening
4. Have an EDSS score of 0 to 4, inclusive
5. Have MFIS ≥ 38 or FSS ≥ 36 , BDI-II ≤ 19 , and ESS ≤ 9
6. Women of childbearing potential must employ proven methods to prevent pregnancy during the course of the trial
7. Able to understand the purpose and risks of the study
8. Must be willing to sign an informed consent
9. Must be willing to follow the protocol requirements
10. Subject must agree not to receive any live or live-attenuated vaccine during the trial

Exclusion Criteria

Candidates will be excluded from study entry or participation if **any** of the following exclusion criteria exist at any time during the study:

1. Have any of the contraindications for Acthar Gel as listed in the approved label, including sensitivity to proteins of porcine origin.
2. Had treatment of systemic or oral corticosteroids of any type in 90 days prior to baseline/randomization
3. Had a relapse or documented objective neurologic worsening in 90 days prior to baseline/randomization
4. Has concurrent neurological disease other than multiple sclerosis
5.
 - a. Any history of sleep apnea
 - b. History (within the last 90 days) of nocturnal pain and/or nocturnal spasms that interferes with or interrupts sleep, or uncontrolled nocturnal restless leg syndrome
6. History of psychosis, bipolar disorder, mania/hypomania
7. History of coronary heart disease, congestive heart failure, chronic pulmonary disease, emphysema, anemia, bleeding disorder, gastrointestinal bleeding, intestinal ulcer, clinically significant cardiac arrhythmia, Type I or II diabetes, uncontrolled hypertension, seizure disorder, cardiac arrhythmia, immune deficiency disorder, HIV-AIDS, tuberculosis, or dysthyroidal state (patients with a history of hypothyroidism or hyperthyroidism, which has been corrected to physiological levels will not be excluded)
8. History of substance abuse, other than tobacco within the past 5 years or current alcohol dependence

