Data forms will be faxed to the data coordination center within 3 business days after each study visit and processed by staff trained in data entry procedures. The forms will be entered by two staff working independently. The completeness of the data and whether the data values are in an appropriate range will be checked periodically. Study sites will be asked to complete data clarification requests for confirmation of missing data or questionable information.

Statistical/Analytical Plan

Primary endpoint

Statistical analysis will be performed to test the change from baseline to end of study in two fatigue measures (MFIS and FSS) to be completed by patient at baseline, Week 8, Week 16, Week 24, and Week 28.

Secondary endpoint

Statistical analysis will be done to test the change from baseline to end of study in depression, sleepiness, and quality of life measures (BDI-II, ESS, and SF-36) to be completed by patient at baseline, Week 8, Week 16, Week 24, and Week 28.

All AEs are to be coded and grouped by organ system. AEs will also be tabulated by severity and by relationship and summarized by treatment group. Summary tables of the AEs will be presented to show the incidence and frequency by treatment group and by study site.

Statistical method

This study will collect longitudinal data that consists of repeated measures on each individual. The mixed-effects regression model for the analysis of longitudinal data will be used to test the changes of the fatigue scores over time.

Sample Size Justification

Ninety subjects will be recruited and randomized 1:1 to receive ACTH or placebo in a subject and examining physician-blinded manner. If the MFIS score decreases from 38 for about 20% with standard deviation =16.4 in the 45 patients who received ACTH, the power to reject the null hypothesis in a paired t-test with alpha=0.5 would be 86%. If the difference of the changes of MFIS score between two treatment group is 7.6 with within group standard deviation=16.4 in the 90 patients, the power to reject the null hypothesis in a t-test with alpha= 0.5 would be 87%. Ziemssen and colleagues (Ziemssen, Hoffman, Apfel, & Kern, 2008) studied the effect of glatiramer acetate on fatigue in MS patients. Glatiramer acetate was found to be associated with a reduction in absence from work and a significant reduction in fatigue symptoms, as measured by MFIS. The data from Ziemssen et al. were used for the sample size calculation for this study.

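### The primary MFIS and FSS test is described as change from baseline with no baseline adjustment specified, which leaves room for a less precise comparison than the data allow

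*Combined protocol and SAP*

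**What the plan says.** All references are to section C of the combined protocol and SAP.

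- **Statistical/Analytical Plan, Primary endpoint:** the test is stated in one sentence, "Statistical analysis will be performed to test the change from baseline to end of study in two fatigue measures (MFIS and FSS"), with both scales "to be completed by patient at baseline, Week 8, Week 16, Week 24, and Week 28". The Secondary endpoint paragraph treats BDI-II, ESS and SF-36 in the same way.
- **Statistical method:** "The mixed-effects regression model for the analysis of longitudinal data will be used to test the changes of the fatigue scores over time". No fixed effects, covariates, random effects, covariance structure or test contrast are named. Nothing says whether baseline is a covariate or one of the responses.
- **Sample Size Justification:** the only place where a between-arm comparison is written out, as a t-test on changes: "If the difference of the changes of MFIS score between two treatment group is 7.6 with within group standard deviation=16.4 in the 90 patients".
- **Inclusion Criteria, item 5:** "Have MFIS ≥ 38 or FSS ≥ 36". A patient can qualify on FSS with an MFIS below 38.
- **Randomization/Treatment assignment and blinding:** stratified by study site only, not by fatigue score.
- **Study Flowchart and Visit 2:** MFIS and FSS are scheduled for every patient at the baseline visit.

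**The concern.** Each statement about the primary comparison is framed as change from baseline, and none brings in the baseline score as an adjustment. A team that follows the text literally could put baseline in the response vector with a separate mean for each arm. With categorical visits and complete data, the treatment contrast at the last visit is then the difference in raw changes.

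Two things are lost:

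- **Precision.** With equal variances, the change-score contrast has a larger variance than the adjusted one whenever r is below 1.
- **Protection against chance imbalance.** If one arm starts d points higher, only r × d of that is expected to persist, but the change score subtracts all of d. The estimate moves by (1 − r) × d in favour of the arm that began more fatigued. Nothing in the randomisation balances baseline fatigue, and the either/or entry rule allows baseline MFIS to vary widely.

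If baseline's role stays open, it can also be settled after the data are seen, between options that differ in precision.

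**Working it through.** **Inputs.** Difference in MFIS change 7.6 (20% of 38), within-group SD 16.4 and 90 patients at 1:1, so 45 per arm (Sample Size Justification). Two-sided alpha 0.05 and 20% dropout, so 0.8 × 45 = 36 per arm (Patient Recruitment). r is **not in the documents**; 0.3 to 0.8 is assumed. The plan does not say whether 16.4 is the SD of change or of the score, so both readings are worked.

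**1. The plan's own figures.** The paired within-ACTH power of 86% reproduces at n = 45, two-sided 0.05 (86.0%). For the two-group test, "the power to reject the null hypothesis in a t-test with alpha= 0.5 would be 87" per cent does not reproduce at 45 per arm:

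- SE = 16.4 × √(2/45) = 3.46; noncentrality = 7.6/3.46 = 2.20; 88 df; power 58.5%.
- At the printed alpha of 0.5, two-sided, power is 93.8%.
- With 90 *per arm* at two-sided 0.05, it is 87.1%.

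That discrepancy is a separate matter. The starting point here is 58.5%.

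**2. Variance ratio.** With equal variances σ²:

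- Var(change) = 2σ²(1 − r)
- Var(adjusted) = σ²(1 − r²)
- Ratio = (1 + r)/2, a reduction of (1 − r)/2: 35%, 25%, 15% and 10% at r = 0.3, 0.5, 0.7 and 0.8.

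**3. Does the mixed model alone deliver this?** Generalised least squares on five visits (compound symmetry, complete data, score SD 16.4, 45 per arm) gives these SEs for the last-visit contrast:

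| r | Raw change | Mixed model, free arm baselines | Mixed model, common baseline | Baseline as covariate |
|---|---|---|---|---|
| 0.3 | 4.09 | 4.09 | 3.30 | 3.30 |
| 0.5 | 3.46 | 3.46 | 2.99 | 2.99 |
| 0.7 | 2.68 | 2.68 | 2.47 | 2.47 |

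So the unstated role of baseline decides which precision is obtained.

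**4. Power if 16.4 is the SD of change** (noncentral t, adjusted SD = 16.4 × √((1 + r)/2)):

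| r | Adjusted SD | 45 per arm | 36 per arm |
|---|---|---|---|
| unadjusted | 16.4 | 58.5% | 49.2% |
| 0.3 | 13.2 | 76.9% | 67.2% |
| 0.5 | 14.2 | 70.9% | 61.0% |
| 0.7 | 15.1 | 65.5% | 55.7% |
| 0.8 | 15.6 | 63.0% | 53.4% |

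**5. Power if 16.4 is the score SD**, 45 per arm, raw change then adjusted: 45.1% to 62.5% (r = 0.3), 58.5% to 70.9% (0.5), 80.1% to 86.1% (0.7), 93.0% to 95.2% (0.8).

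**6. Chance imbalance, with 16.4 as the SD of change.** Score SD = 16.4/√(2(1 − r)). A one-SE baseline difference is score SD × √(2/45), and the raw-change estimate shifts by (1 − r) times that.

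- r = 0.5: score SD 16.4; SE 3.46; shift 0.5 × 3.46 = 1.7 points (23% of 7.6).
- r = 0.7: score SD 21.2; SE 4.46; shift 0.3 × 4.46 = 1.3 points (18% of 7.6).

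**The case against.** The strongest reply is that the text does not commit the trial to an unadjusted analysis. Testing change from baseline names a quantity of interest. Analysis of covariance on change gives the same treatment estimate as on the final score, so an adjusted model fits the sentence too. The visit list says when the scales are completed, not which values form the response vector. Changes over time could also mean a treatment-by-time slope, whose contrast is not the baseline-to-end difference. The equality in step 3 needs categorical visits, free arm baselines and complete data, and the plan itself expects 20% dropout.

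This stands. A reader might infer that the primary analysis *is* raw change with no adjustment, but no sentence says so. The documents support only that no adjustment is specified and that a literal implementation can end up there.

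A reader might also infer that the test would be biased or invalid. It would not be: under randomisation the raw-change comparison is unbiased on average and keeps its type I error. Over-correction is conditional on the imbalance actually observed.

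The gain also depends on unknowns. At r = 0.8 the variance falls by only 10%, and if 16.4 is the score SD, power moves only from 93.0% to 95.2% there. This limits the size of the gain. It does not reverse its direction anywhere in the range examined.

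**Conclusion.** The point holds as one of specification and efficiency, not validity. The plan frames the primary test as change from baseline, names a mixed model, and leaves the role of baseline open. One natural implementation gives up 35% to 10% of the variance for r from 0.3 to 0.8, assuming equal variances.

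If 16.4 is the SD of change, adjustment raises power from 58.5% to 77%–63% at 45 per arm, and from 49% to 67%–53% at 36 per arm. If it is the score SD, the rise at 45 per arm is from 58.5% to 70.9% at r = 0.5 and from 80.1% to 86.1% at r = 0.7.

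It would be wrong to read this as a rescue of the sample size. If 16.4 is the SD of change, no r in the assumed range reaches 80% power at 45 per arm, and the stated 87% needs its own correction. The change should still be made, because it uses scores already scheduled for every patient and fixes the choice in advance.

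**What to change.** In the Statistical/Analytical Plan, state for MFIS and for FSS that post-baseline scores are modelled with treatment, visit, treatment-by-visit, the same scale's baseline score and baseline-by-visit. Alternatively, keep baseline as a response and constrain the two arms to one common baseline mean. Name the end-of-study visit and test the treatment contrast there. Use the same form for BDI-II, ESS and SF-36.

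**Cost.** With four post-baseline visits, baseline plus baseline-by-visit takes about four parameters per scale. The text sits in the protocol, so this is a wording amendment, which under Regulatory Requirements (section D) needs approval by the Providence IRB and each site's IRB/IEC. No new data, visits or patients are needed.

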Review of medical history, physical exam, Modified Fatigue Impact Scale (MFIS), Fatigue Severity Scale (FSS), Epworth Sleepiness Scale (ESS), Beck Depression Inventory-II (BDI-II) and Expanded Disability Status Scale (EDSS) will be performed at screening to assess the eligibility of the patient, and the Columbia-Suicide Severity Rating Scale will be administered. The outcome measures, including MFIS, FSS, BDI-II, ESS, and SF-36, will be administered at baseline, week 8, week 16, week 24, and week 28 which is 4 weeks after the last ACTH or placebo dose. In addition, office visits with the treating physician will be conducted at the same interval for physical exam, review of concomitant medications and adverse events, and monitoring of patient safety and eligibility, and administration of the C-SSR. Laboratory tests will be performed at the time of study visits. A separate serum sample (7 ml SST tube) will be collected at baseline, week 16, and week 28. This sample will be stored at -20c until shipped to the coordinating center. The specimen will then be stored at the study coordinating center for future research use.

STUDY FLOWCHART

ACTH for MS fatigue							
	Screening	Baseline	Follow-up Evaluations				Premature Termination
Visit #	1	2	3	4	5	6	
Week	-4 to -1	0 (±4days)	8 (±4days)	16 (±4days)	24 (±4days)	28 (±4days)	
Informed Consent & Demographics	X						
Randomization		X					
Medical & Neurological History	X	X	X	X	X	X	X
Physical & Neurologic Exam	X	X	X	X	X	X	X
Vital Signs	X	X	X	X	X	X	X
ECG	X						
Laboratory Assessments							
• Urinalysis	X	X	X	X	X	X	X
• CBC	X	X	X	X	X	X	X
• CMP	X	X	X	X	X	X	X
• TSH	X						
• Pregnancy Test/HCG (for female only)	X	X	X	X	X		
Additional Serum Sample for Research Purposes		X		X		X	
EDSS	X						
MFIS, FSS, BDI-II, ESS, SF36	X	X	X	X	X	X	X
C-SSR	X	X	X	X	X	X	X
Study Drug Dispensing		X	X	X			
Protocol Compliance & Study Drug Accountability		X	X	X	X	X	
Concomitant Therapy and AEs	Monitor and record throughout the study						

Informed consent

The investigator or designated research staff will obtain informed consent from each subject after explaining the purpose of the study and the potential risks and benefits known or can be reasonably expected. The IRB approved informed consent form will be signed by the subject or the legal representative before the subject participates in any study procedure. The original signed informed consent form will be kept in the subject's medical record, a duplicate will be provided to the subject.

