
Visit 1 or Screening visit (Week -4 to -1; 7 to 28 days prior to Baseline)

The following clinical and laboratory evaluations will occur within 4 weeks prior to baseline. The investigator/treating neurologist (or designee where allowed) must perform all screening evaluations to determine patient eligibility.

- Informed consent
- Demographics
- Review of medical and neurological history
- Review of medications
- Vital signs
- Physical and neurological exam
- EDSS
- ECG
- Laboratory assessments: Urinalysis, CBC, CMP, TSH, Pregnancy test/HCG (female only)
- MFIS, FSS, BDI-II, ESS, SF36, C-SSR*

* The C-SSR must be reviewed by the site principal investigator or treating physician prior to the patient leaving the clinic

Visit 2 or Baseline visit (Week 0; 4 weeks after Screening +/- 4 days)

The following clinical and laboratory evaluations will occur at baseline visit, which must be completed 4 weeks after screening (+/- 4 days). The investigator/treating neurologist will review inclusion/exclusion criteria to confirm patient eligibility before study drug is dispensed.

- Randomization
- Interval medical and neurological history
- Vital signs
- Physical and neurological exam
- Laboratory assessments: CBC Urinalysis, CMP, Pregnancy test/HCG (female only)
- MFIS, FSS, BDI-II, ESS, SF36, C-SSR*
- Study drug dispensing
- Protocol compliance study drug accountability
- Concomitant therapy and AEs
- Additional serum sample for research purposes

* The C-SSR must be reviewed by the site principal investigator or treating physician prior to the patient leaving the clinic

Visit 3/Week 8 (8 weeks +/- 4 days from baseline)

The following clinical and laboratory evaluations will occur 8 weeks after baseline with a +/- 4 day window. The investigator/treating neurologist will review inclusion/exclusion criteria to confirm patient eligibility before study drug is dispensed.

- Interval medical and neurological history
- Vital signs
- Physical and neurological exam
- Laboratory assessments: CBC, Urinalysis, CMP, Pregnancy test/HCG (female only)
- MFIS, FSS, BDI-II, ESS, SF36, C-SSR*
- Study drug dispensing
- Protocol compliance study drug accountability
- Concomitant therapy and AEs
- Additional serum sample for research purposes

* The C-SSR must be reviewed by the site principal investigator or treating physician prior to the patient leaving the clinic

Visit 4/Week 16 (16 weeks +/- 4 days from baseline)

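### Screening scores on all five outcome scales are collected but given no role in the analysis; entering them as a second pre-treatment covariate is a free, probably small, gain in precision

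*Combined protocol and SAP*

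**What the plan says.** The study flowchart lists MFIS, FSS, BDI-II, ESS and SF-36 at screening and at baseline. The Visit 1 and Visit 2 lists agree, each carrying the entry "MFIS, FSS, BDI-II, ESS, SF36, C-SSR". Every randomised patient should therefore have two pre-treatment scores per scale.

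The narrative under Laboratory Testing and Study Procedure says of the screening assessments, including MFIS, FSS, ESS and BDI-II, that they "will be performed at screening to assess the eligibility of the patient". It then describes the analysed series: "The outcome measures, including MFIS, FSS, BDI-II, ESS, and SF-36, will be administered at baseline, week 8, week 16, week 24, and week 28". SF-36 is missing from that narrative's screening list, although the flowchart and the Visit 1 list include it. No eligibility criterion uses SF-36, so its screening score has no stated use at all.

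Under Statistical/Analytical Plan, the primary endpoint paragraph reads "Statistical analysis will be performed to test the change from baseline to end of study in two fatigue measures (MFIS and FSS" and names baseline and Weeks 8, 16, 24 and 28. The secondary endpoint paragraph follows the same pattern. The method is one sentence: "The mixed-effects regression model for the analysis of longitudinal data will be used to test the changes of the fatigue scores over time". It does not say whether the Week 0 score is a covariate or a response, and it does not mention the screening score.

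**The concern.** A single self-reported fatigue score is partly noise from the day it was taken. A second pre-treatment score can remove some of that noise from the comparison between arms, and here it is already collected and paid for. Precision matters in this trial because, on the plan's own inputs, the between-group test has well under the power claimed for it (see the working), and withdrawn patients are not replaced. At stake is a somewhat wider confidence interval than necessary. The validity of the comparison is not in question.

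**Working it through.** **Inputs.** From Sample Size Justification: difference in MFIS change 7.6, within-group SD 16.4, 90 patients randomised 1:1 (45 per arm). From Patient Recruitment: two-sided alpha 0.05 and 20% dropout. Sample Size Justification prints alpha as 0.5; I use 0.05. Assumptions: 16.4 is the SD of change, and the correlations between occasions are as stated below, since the documents give none.

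**The plan's figure.** The plan states 87% power. The noncentrality is 7.6 / (16.4 × √(2/45)) = 2.20, and the noncentral t on 88 df gives 58%. With 36 per arm (45 × 0.8) it is 49%. The 87% appears only with 90 patients per arm (87.1%). Read literally, alpha 0.5 gives 94%.

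**Equal correlation r between all occasions.** With unit score variance:
- raw change: variance 2(1 − r)
- Week 0 as covariate: residual variance 1 − r²
- Week 0 plus screening: residual variance 1 − 2r²/(1 + r)
- ratio of the last two: (1 + 2r)/(1 + r)²

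Scaling so that the SD of change is 16.4 gives a score SD of 16.4/√(2(1 − r)). Power below is for 45 per arm, with one df taken off per covariate:

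| r | Week 0 only | Week 0 + screening | variance ratio |
|---|---|---|---|
| 0.5 | 70.9% | 75.9% | 0.889 |
| 0.6 | 68.1% | 74.6% | 0.859 |
| 0.7 | 65.5% | 73.5% | 0.830 |
| 0.8 | 63.0% | 72.5% | 0.802 |

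The screening score adds 5-10 points and removes 11-20% of residual variance. The step from 58% to 63-71% comes from ordinary Week 0 adjustment and is not part of this point. At 36 per arm and r = 0.7 the step is 56% to 64%. At r = 0.3 it is about 2 points.

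**Correlation that decays with time.** Equal correlation requires screening to predict Week 24 as well as Week 0 does. Let r be the Week 0-outcome correlation, q screening-outcome and s screening-Week 0. Then R² = (r² + q² − 2rqs)/(1 − s²), compared with r² for Week 0 alone.
- r = 0.6, q = 0.55, s = 0.7: R² = 0.2005/0.51 = 0.393; ratio 0.607/0.64 = 0.948, a 5% reduction.
- r = 0.6, q = 0.50, s = 0.7: R² = 0.19/0.51 = 0.373; ratio 0.980, a 2% reduction.
- r = 0.6, q = 0.50, s = 0.8: R² = 0.13/0.36 = 0.361; ratio 0.998, a 0.2% reduction.
- r = 0.6, q = 0.42, s = 0.7: R² = 0.1836/0.51 = 0.360; no gain.

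The general condition for no gain is q = r × s; in the last line, 0.6 × 0.7 = 0.42.

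**Decay and entry selection together.** Simulation used a stable trait, an autoregressive part with a half-life of 6-12 weeks, occasion noise at 10-20% of variance, and an entry threshold at or 0.5 SD below the population mean. The residual variance fell by about 1-6%. With no decay (trait plus 30% noise) it fell by 10-12%. In power terms, at r = 0.7 the Week 0-only noncentrality is 7.6/(15.12 × √(2/45)) = 2.384. A 6% reduction makes it 2.384/√0.94 = 2.459, and power goes from 65.5% to 68.2%. A 1% reduction adds about 0.4 points.

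**Covariate or average.** Averaging the two scores gives a change variance of 1 + (1 + s)/2 − (r + q). At r = 0.6, q = 0.42, s = 0.7 this is 0.83, against 2(1 − 0.6) = 0.80 for Week 0 alone. Averaging would make the change about 4% more variable where a covariate costs only a degree of freedom.

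**The case against.** The strongest reply is that this is a refinement and not an error. Measuring change from the pre-dose visit is ordinary practice, and nothing in the plan is biased or contradictory because the screening score goes unused. That stands. It also stands that the plan never excludes the screening score: a reader might infer a rule that Week 0 alone is used, but this is read from the listed time points, and the stated eligibility purpose is not said to be the only one. The larger gap is that the model's handling of baseline is unspecified.

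The size is open to challenge too. A reader might take 5-10 points of power as the expected gain. The documents do not support that, since they give no correlations and the figure needs screening to predict Week 24 as well as Week 0 does. Nor is occasion noise in the scores enough to guarantee a gain: the 0.8/0.6/0.5 pattern above leaves 0.2%.

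The arithmetic is for MFIS only. BDI-II ≤ 19 and ESS ≤ 9 are mandatory ceilings, unlike the either/or rule for MFIS and FSS, so range restriction on those scales differs and the result cannot be carried over. Finally, the plan does not say whether 16.4 is the SD of change or of a single score. If it is a single-score SD, adjusted power at r = 0.7 goes from 87% to 92% (normal approximation), and that adjusted analysis would not be underpowered at 45 per arm.

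None of this shows the change to be harmful or costly. Selection on MFIS ≥ 38 or FSS ≥ 36 raises the screening score in both arms alike, and the score precedes randomisation, so covariate adjustment introduces no bias into the contrast.

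**Conclusion.** The point holds as a free improvement in precision. Two pre-treatment scores exist on each outcome scale, and the analysis section gives the screening one no role. For MFIS, the gain beyond Week 0 adjustment is most plausibly about 1-6% of residual variance, or roughly 0.5-3 points of power at 45 per arm. It could reach about 12% without decay, or 11-20% under equal correlation of 0.5-0.8, and it is nil when the screening-outcome correlation equals the product of the other two. All of these rest on assumed correlations. The benefit to the secondary scales is unquantified.

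A reader might also infer that the second covariate cures the power shortfall. It does not: if 16.4 is the SD of change and correlations are 0.5-0.8, power stays below 80% even in the most favourable case. The gap between the stated 87% and the recomputed 58% needs its own correction.

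**What to change.** Add one sentence to Statistical/Analytical Plan: the mixed model for each scale's post-baseline scores includes both the screening and the Week 0 score of that scale as separate covariates, for MFIS, FSS, BDI-II, ESS and SF-36. This also settles that Week 0 enters as a covariate and not as a response. Do not average the two scores into the change, because entry selection raises the screening score and averaging can add variance. Fix the choice before unblinding, so that one or two covariates is not a post hoc decision.

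The cost is one degree of freedom per model, with no new data, visits or patient burden. The visit headings should be reconciled at the same time, because the gap between the two scores affects how much the first adds: "Visit 1 or Screening visit (Week -4 to -1; 7 to 28 days prior to Baseline" allows 7 to 28 days, while "Visit 2 or Baseline visit (Week 0; 4 weeks after Screening +/- 4 days" implies 24 to 32 days (28 ± 4).

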The following clinical and laboratory evaluations will occur 16 weeks after baseline with a +/- 4 day window. The investigator/treating neurologist will review inclusion/exclusion criteria to confirm patient eligibility before study drug is dispensed.

- Interval medical and neurological history
- Vital signs
- Physical and neurological exam
- Laboratory assessments: CBC, Urinalysis, CMP, Pregnancy test/HCG (female only)
- MFIS, FSS, BDI-II, ESS, SF36, C-SSR*
- Study drug dispensing
- Protocol compliance study drug accountability
- Concomitant therapy and AEs
- Additional serum sample for research purposes

* The C-SSR must be reviewed by the site principal investigator or treating physician prior to the patient leaving the clinic

Visit 5/Week 24 (24 weeks +/- 4 days from baseline)

The following clinical and laboratory evaluations will occur 24 weeks after baseline with a +/- 4 day window. The investigator/treating neurologist will review inclusion/exclusion criteria to confirm patient eligibility.

- Interval medical and neurological history
- Vital signs
- Physical and neurological exam
- Laboratory assessments: CBC, Urinalysis, CMP, Pregnancy test/HCG (female only)
- MFIS, FSS, BDI-II, ESS, SF36, C-SSR*
- Protocol compliance study drug accountability
- Concomitant therapy and AEs

- Additional serum sample for research purposes

* The C-SSR must be reviewed by the site principal investigator or treating physician prior to the patient leaving the clinic

Visit 6/Week 28 (28 weeks +/- 4 days from baseline)

The following clinical and laboratory evaluations will occur 28 weeks after baseline with a +/- 4 day window.

- Interval medical and neurological history
- Vital signs
- Physical and neurological exam
- Laboratory assessments: CBC, Urinalysis, CMP
- MFIS, FSS, BDI-II, ESS, SF36, C-SSR*
- Protocol compliance study drug accountability
- Concomitant therapy and AEs
- Additional serum sample for research purposes

* The C-SSR must be reviewed by the site principal investigator or treating physician prior to the patient leaving the clinic

Premature termination visit

If discontinuation of study drug occurs, a premature termination visit must be performed as soon as possible, or within 7 days after the last dose of study drug. Randomized patients who were withdrawn from the study for any reason will not be replaced. The following clinical and laboratory evaluations will be performed:

- Interval medical and neurological history
- Vital signs

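### The power figures make no allowance for the planned 20% dropout; the 86% is a within-arm figure (about 77% with 36 completers), and the between-arm 87% is about 58%, or 49% after dropout

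*Combined protocol and SAP*

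**What the plan says.** Three places in the Combined protocol and SAP bear on this.

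- **Patient Recruitment** says the sample size came from a power analysis for a two-sided test at alpha 0.05, "and power = 0.80 and assuming a 20% dropout rate". It names no test, arm, effect size or standard deviation.
- **Sample Size Justification** gives two power figures. The first is within one arm. It starts "If the MFIS score decreases from 38 for about 20" per cent, "with standard deviation =16.4 in the 45 patients who received ACTH", and concludes that "the power to reject the null hypothesis in a paired t-test with alpha=0.5 would be 86" per cent. The second takes a difference in MFIS change of 7.6 between groups, a within-group SD of 16.4 and 90 patients, and reports 87%, again printing alpha as 0.5. Neither mentions dropout.
- **Premature termination visit** says: "Randomized patients who were withdrawn from the study for any reason will not be replaced".

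Specific Aims and Endpoints both state the primary objective as the efficacy of ACTH compared with placebo.

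**The concern.** The allocation is stated as "Ninety subjects will be recruited and randomized 1:1 to receive ACTH or placebo", so 45 is the full ACTH arm. A power figure based on all 45 contains no loss, although the plan expects to lose one patient in five and will not replace them.

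The 86% also answers a different question from the trial's. A before-after test in the ACTH arm cannot separate drug effect from placebo response. Nor can it separate it from regression to the mean, which is to be expected when patients enter on high fatigue scores (MFIS at least 38 or FSS at least 36).

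At stake is whether a reader can rely on this section to justify 90 patients. The 86% is the only one of its two figures that reproduces from the printed inputs once alpha is read as 0.05, so it is the one a reader might fall back on.

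**Working it through.** **Inputs.** Change = 20% of 38 = 7.6 MFIS points; SD = 16.4; 90 randomised 1:1, so 45 per arm (all from Sample Size Justification). Two-sided alpha 0.05 and 20% dropout (Patient Recruitment). Evaluable per arm after dropout = 45 × 0.8 = 36. Assumption: 16.4 is the SD of the change. Standardised effect = 7.6 / 16.4 = 0.463.

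**Step 1: reproduce the 86%.** Paired t-test by the noncentral t distribution, with df = n − 1 and noncentrality = 0.463 × √n.

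| n | alpha (two-sided) | noncentrality | power |
|---|---|---|---|
| 45 | 0.05 | 3.109 | 86.0% |
| 44 | 0.05 | 3.074 | 85.2% |
| 46 | 0.05 | 3.143 | 86.8% |
| 45 | 0.5 (as printed) | 3.109 | 99.2% |

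The printed figure is therefore the n = 45 result at alpha 0.05. It carries no dropout allowance, and the printed 0.5 is not the value that was used.

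**Step 2: apply the plan's dropout to the same test.** With n = 36, noncentrality = 0.463 × 6 = 2.780 and power = 77.1% (79.4% by the normal approximation). For this test, 80% power needs 39 evaluable patients (38 give 79.4% by noncentral t). That is 39 / 0.8 = 48.75, so 49 randomised per arm.

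**Step 3: the comparison that matches the objective.** Two-sample t-test, df = 2n − 2, noncentrality = 7.6 / (16.4 × √(2/n)), two-sided alpha 0.05.

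| n per arm | noncentrality | power |
|---|---|---|
| 45 | 2.198 | 58.5% |
| 36 | 1.966 | 49.2% |
| 75 | 2.838 | 80.5% |
| 90 | 3.109 | 87.1% |

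The printed 87% is the result for 90 patients in each arm, not 90 in total. The printed alpha does not explain it either: at two-sided 0.5 with 45 per arm, power is 93.8%. On these inputs, 80% needs 75 evaluable per arm, or 75 / 0.8 = 93.75, so 94 randomised per arm.

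**Step 4: check the SD assumption.** Suppose 16.4 were instead the SD of a single score, with correlation r between visits. The SD of the change would then be 16.4 × √(2(1 − r)). At r = 0.5 this equals 16.4 and nothing changes. At r = 0.7 it is 12.7, and between-arm power is 80.1% with 45 per arm and 70.7% with 36. But the paired power at n = 45 would then be 97.5%, not 86%. The printed 86% fits only if 16.4 is used as the SD of the change.

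**The case against.** Several points on the other side have force.

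- **The 80% is not tied to the paired test.** Patient Recruitment does not say which test its 80% belongs to. A reader might infer that the plan's own 80% claim is refuted because the within-arm figure falls to 77%. The documents do not make that link. They support only that the two sections do not agree and need reconciling.
- **How 90 was derived is not shown.** A reader might infer that dropout was ignored throughout. What can be said is that neither printed power figure includes it; the calculation behind Patient Recruitment is not given.
- **The shortfall of the within-arm figure is narrow.** The normal approximation gives 79.4%. The plan says about 20%, and at n = 36 a change of 7.9 points gives 80.2%. If mean baseline MFIS were 40 (an assumption), 20% would be 8.0 points and power 81.2%.
- **Completers only is not the planned analysis.** Statistical method specifies a mixed-effects model on repeated measures, and MFIS is collected at the premature termination visit. Patients who leave can contribute data, so reading 77% or 49% as the power the trial will actually have goes too far.
- **The within-arm figure is secondary.** If it is deleted, whether it was 86% or 77% decides nothing.

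The first four limit what can be claimed for 77%. The last is right, and is why the correction cannot stop at the within-arm figure. None of them rescues the 87%: even with no dropout at all, 45 per arm gives about 58%. The plan justifies its size with t-tests and offers no calculation for the mixed model.

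**Conclusion.** The point holds in this form. Sample Size Justification makes no allowance for the 20% dropout stated in Patient Recruitment. Its 86% is the power of a paired test on all 45 ACTH patients at two-sided alpha 0.05, misprinted as 0.5. With 36 completers it is about 77%, and it does not bear on ACTH versus placebo in either case. The larger gap is in the comparison that does: about 58% with 45 per arm and about 49% with 36, against a printed 87% that corresponds to 90 per arm.

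The arithmetic is firm given a change or difference of 7.6, 16.4 as the SD of the change, and alpha 0.05. The figures at 36 per arm also treat patients who leave as contributing nothing, so they do not predict the power of the mixed model.

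**What to change.** In Sample Size Justification:

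1. Delete the within-arm figure, or label it descriptive and restate it as about 77% with 36 evaluable patients.
2. Correct alpha to 0.05, two-sided, in both power statements.
3. Replace the 87% with the between-arm power: about 58% with no dropout and about 49% with 36 evaluable per arm. State that 16.4 is taken as the SD of the change.

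In Patient Recruitment, reconcile the statement of 80% power with 20% dropout with these figures. If the sponsor expects the mixed model to recover power from partial data, that calculation and its assumptions should be shown.

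This changes wording only; no procedure or analysis is altered. The cost is that the stated power becomes clearly less favourable.
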